The effect of silver diamine fluoride (SDF) on bacteria involved in root or cervical carious lesions using HOMINGS technology. A clinical study

[name]

Version 2.0

11 November 2016

Thesis Committee:

[name], PhD, Chair

[name], MS

[name], MS

[name], Department of Microbiology, The Forsyth Institute,
Cambridge, MA

Introduction:

The World Health Organization recommends that countries urgently need to adopt strategies for improving the oral health of elderly populations and recognizes that there is a universal need for prevention of oral diseases such as root caries.¹ Root caries is common in institutionalized elders and periodontal patients with exposed root surfaces. Effective prevention methods are needed.² The use of fluoride releasing agents as a means of preventing dental caries has long been recognized, and amongst these agents silver diamine fluoride (SDF) has received considerable attention as a caries-controlling agent of choice.³

Clinical trials have demonstrated that silver diamine fluoride (SDF) can arrest caries.⁴⁻⁶ However, the mechanism of action is not yet fully known.⁷ Previous studies on the mechanisms of SDF have mostly focused on limited antimicrobial effects and mineral changes in tooth structure.⁷⁻⁹ SDF is used in many countries and has been approved in the USA as “Advantage Arrest” manufactured by Elevate Oral Care company.

SDF contains high concentrations of silver and fluoride ions which can inhibit the growth of multi-species cariogenic biofilms.¹⁰ The concentration

of 38% silver diamine fluoride (SDF) has been documented to arrest dental caries by reducing the demineralization process.¹¹⁻¹⁶ SDF is a clear liquid. Several studies in children reported that in rare cases SDF might cause gingival/mucosal irritation, which heals spontaneously within 48 hours.^{11,17-19} Most studies recommend using SDF once a year to arrest caries, but applications every 6 months, or once every 2-3 years have also been tested. Furthermore, the need for maintaining salivary function and oral hygiene has been emphasized to avoid reactivation of treated caries. In 2016, Deutsch reported that caries lesions might reactivate within the year if salivary function and oral hygiene is poor.²⁰

A literature review of SDF suggested that 38% SDF can be an effective agent in preventing new caries and arresting dental caries in the primary teeth of children.²¹ Another review concluded that SDF is an effective, efficient, and equitable caries-control agent.²² Milgrom and Chi (2011) advocated SDF therapy as an important prevention-centered caries management strategy during critical early childhood periods.²³ The clinical trial by dos Santos et al. (2012) concluded that 38 % SDF was better than interim restorative treatment with a glass ionomer for arresting cavitated lesions in early childhood caries (ECC).²⁴

A randomized clinical study used a 38% SDF solution among institutionalized elderly subjects and showed that it was more effective in preventing new root caries lesions than giving oral hygiene instruction (OHI) alone (Tan et al., 2010).³ Another clinical study reported for the first time that synergetic applications of SDF solution and oral health education (OHE) annually was more effective than giving OHI alone in preventing and arresting root caries among community-dwelling elderly subjects. There was a trend of less new root caries development among those who received synergetic applications of SDF and OHE compared to those who received SDF alone.²⁵

Since root caries is caused by plaque bacteria that adhere to exposed root surfaces (Berry et al., 2004), providing instructions on how to improve oral hygiene would theoretically be beneficial.²⁶ Investigating the effects of SDF agents on plaque bacteria will allow better understanding of SDF's mechanism of action on root caries arrest.

The International Caries Detection and Assessment System (ICDAS) will be used to score carious lesions. The ICDAS criteria include early and later stage caries severity, and instructions for standard examination processes. ICDAS includes scores from 0 (sound) to 6 (extensive distinct cavity with visible dentin).

Human Oral Microbe Identification using Next Generation Sequencing (HOMINGS) utilizes the speed and efficiency of next generation sequencing combined with the refinement of species-level identification. Nearly 600 oral bacterial taxa are identified at the Species-level and Genus-level identification of remaining sequences for 129 genera. HOMINGS allows identification and comparison of bacterial associations in oral health and disease, including different types of periodontitis, caries, gingivitis, ventilator-associated pneumonia, endodontic and odontogenic lesions, abscesses, and halitosis. Also, HOMINGS can determine the efficacy of therapies/treatments, e.g., mouth rinses, antibiotic treatment, scaling and root planning, and laser or periodontal surgery. HOMINGS will be utilized for microbial analysis in this study.

Research Question:

What is the mechanism of action of silver diamine fluoride (SDF) on bacteria involved in root or cervical carious lesions using human oral microbe identification microarray (HOMINGS) technology?

Objective:

To **assess** the effect of SDF treatment on a large array of microorganisms present in root or cervical carious lesions using HOMINGS technology. This will be accomplished by assessing microbial deposits on root or cervical caries lesions before and 1 month after SDF application.

Rationale:

Older people that have caries-active disease experience root caries at a rate which is at least as great as that of coronal caries among adolescents.²⁷

The use of fluoride releasing agents as a means of preventing dental caries has long been recognized, and amongst these agents silver diamine fluoride (SDF) has received considerable attention as a caries-arresting agent of choice.²⁸

Silver diamine fluoride outperforms other anticaries medicaments such as chlorhexine, NaOCl-based gel (Carisolv), and an enzyme-based gel (Papacarie) in killing cariogenic bacteria in dentinal tubules, and results in less aversive taste and texture responses than to fluoride varnish.²⁹

38% SDF arrests dental caries producing bacteria such as *Streptococcus mutans*, *Streptococcus sobrinus*, *Lactobacillus acidophilus*, *Lactobacillus rhamnosus* and *Actinomyces naeslundii* by reducing the demineralization process. It minimizes the loss of mineral content and slows down collagen I

destruction. Furthermore, it contains high concentrations of silver and fluoride ions, which may inhibit the growth of multi-species cariogenic biofilms.¹⁰

Safety is an important aspect, which should be considered in the clinical use of SDF solution. An important review considered silver diamine fluoride (SDF) as a safe, effective, efficient, and equitable caries-preventive agent that appears to meet the criteria of the WHO Millennium Goals and the US Institute.^{28, 30} The effect of SDF in preventing dentine collagen degradation from bacterial collagenase challenge has also been well documented.³¹ The germicidal action of the SDF preparation in arresting active caries and contributing to disinfection of root canals has also been documented.³²

There are 3 components of SDF: silver, amine, and fluoride. Silver alone and the more complex silver nitrate have been used for millennia for medical applications. Fluoride is now widely used in a multitude of applications for caries prevention. Unlike the application of fluoride among children, the use of higher concentrations of fluoride among the elderly is acceptable and cannot cause fluorosis.³³

Hypothesis:

H₀: there is no inhibitory effect of bacteria by 38% SDF

H_A: there is an inhibitory effect of bacteria by 38% SDF

Materials and Methods:

Setting: General Dentistry clinics of the University of Michigan School of Dentistry.

Approval from the Internal Review Board Med (IRB) of the University of Michigan will be obtained prior to implementation.

Study Subjects and Screening:

Inclusion Criteria:

- Generally healthy adult participants 18 years of age and older.
- At least one tooth with active (soft) cavitated lesions of ICDAS score 5 or 6 near the gingival margin (coronal cervical caries at the CEJ or exposed root surfaces with soft active carious lesions exposing dentin).

Exclusion Criteria:

- Adult participants who suffer from serious life-threatening medical diseases that interfere with basic daily self care activities.
- Patients taking antibiotics within the last two weeks.
- Patients using chlorhexidine or fluoride mouth washes within the last two weeks.
- Pregnant or breastfeeding women.
- Teeth with arrested (hard) cervical or root caries lesions.
- Teeth that have been diagnosed with an abscess or an irreversible pulpitis, or are mobile.

Generally healthy adult participants 18 years of age and older with at least one tooth with active cavitated lesions of ICDAS score 5 or 6 near the gingival margin (coronal cervical caries at the CEJ or exposed root surfaces with soft active carious lesions exposing dentin) will be recruited by one of the researchers after the IRB approval in the General Dentistry Clinic at the University of Michigan. Other providers in the General Dentistry Clinic, or other departments, will be informed of the eligibility criteria by the study PI personally, via word of mouth, and via study flyers or emails, and can refer potential subjects to the study team. This could occur either at a patient appointment, or via a review of the patient chart (please see request for Waiver of Consent). The PI will approach potential subjects in person or via phone call to assess interest in study participation. If interested, a study appointment will be scheduled and Informed Consent performed.

At the study appointment, patients will be provided with verbal and written information describing the purpose of the study and potential side effects (lesions will turn black). They will be informed that all information is confidential and that they can freely withdraw at any time during their participation. They will have the opportunity to ask questions related to the study. After obtaining written informed consent, study subjects will be examined by the study PI. Status of the cervical or root caries lesions will be assessed by visual inspection and aided by tactile detection using a probe. Decay- missing- filled teeth (DMFT) index will be assessed for each patient at the initial visit. We will also use ICDAS sensitivity and specificity criteria scores 5 and 6. Score 5 is a distinct cavity with visible dentin; frank cavitation involving less than half of a tooth surface. Score 6 is an extensive distinct cavity with dentin; cavity is deep and wide involving more than half of a tooth surface.

Food particles obscuring visual inspection of root or cervical surfaces will be removed. Two surfaces per tooth (buccal and lingual) will be examined clinically for root surface caries. Individualized oral hygiene instructions will be provided to each participant, focusing on effective brushing with a manual toothbrush, and use of fluoride toothpaste will be recommended.

[figure not shown]
Treatment:

Eligible study subjects will have plaque collected from 1 randomly selected caries lesion that meets the inclusion criteria. Before applications of the study agent, a piece of gauze will be used to dry the teeth. Bacterial samples from subjects' root or cervical carious lesions will be collected with sterile Gracey curettes via a gentle scraping movement.^{34,35} Samples will be collected at the beginning of each appointment, but following consent and eligibility review. Samples will be frozen until analyses. The SDF solution will then be applied onto the exposed root surfaces of participants by means of a disposable microbrush following the manufacturer's recommendation by using their specialized Advantage Arrest applicator. The applicator will not absorb the product as it applies, and there is no risk of leaving flock portions of the applicator on the site. The surface tension of the material being applied holds the liquid on the applicator until it contacts the application site. The participants will be instructed not to eat or drink for one hour after treatment. Patients will be asked to return 1 month later. At this time, the lesions will be assessed for changes in hardness and color, and then a second microbial sample will be collected as described below and frozen until analyses.

Sample Size:

A sample including 20 subjects is decided to constitute the study sample. Samples will be collected from each patient at the first visit and at the one month recall visit.

An additional 2 test plaque samples will be collected for calibration purposes. These will be collected either from subjects who will also participate in the main project or 2 additional subjects. Plaque sampling on the two test subjects will be for calibration purposes, to ensure the sampling technique yields samples with sufficient volume to reliably extract bacterial DNA.

Patient Participation:

Test Sample Collection (2 subjects):

- 1/Consent form and Eligibility review
- 2/Questionnaire
- 3/Examination and diagnosis for root surface caries (photographs when possible)
- 4/Bacterial sample collection

1st appointment:

- 1/Consent form and Eligibility review
- 2/Questionnaire
- 3/Examination and diagnosis for root surface caries (Pre-SDF photographs when possible)
- 4/Bacterial sample collection
- 5/SDF application
- 6/Post-SDF application photograph

2nd appointment (one month recall):

- 1/Questionnaire
- 2/Examination and diagnosis for root or cervical surface caries to confirm if caries still exist (Photographs when possible)

3/Bacterial sample collection

Outcome Measures and its Assessment:

Patients will be seen twice, at baseline and at one-month recall, to compare the microbial composition of bacterial samples at the two different stages. Also, questionnaires will be completed by the patients at baseline and after one month to collect information on tooth brushing behavior, use of fluoride toothpaste, frequency of sweet snack intake between meals. Patients will also be asked about the acceptability of the treatment. Two eligible subjects with multiple eligible lesions will be seen for plaque collection calibration to ensure the plaque sample technique yields adequate volume to extract bacterial DNA for analysis. These subjects can also participate in the baseline and one-month recall, if the subject elects.

Incentives:

1/Participants will be given a toothbrush and toothpaste at the initial visit, and \$10 for their initial participation. We will pay for patient parking for the visit.

2/Fifteen dollars at the one-month recall research clinical visit. We will pay for patient parking at the visit.

3/At the one month recall, if active caries still exists or if the patient does not like the color, patients will be offered an appropriate restoration at our expense at the General Dentistry Clinic at the University of Michigan.

4/Two subjects will also participate in a test plaque sample collection visit. These subjects will receive \$18 for this visit and will receive compensation for patient parking.

Collection and determination of the bacteria involved in the carious lesions:

Gracey curettes will be used to collect plaque samples. Plaque samples will be coded, which will allow the samples to be connected to the overall study data. These samples will be used to identify the types of bacteria involved in the carious lesions and bacteria arrested after the application of the testing material after one month. The microbial composition of the samples will be assessed using human oral microbe identification microarray (HOMINGS). After the bacterial collection, the samples from the cervical or root carious lesions will be suspended in tubes containing 150 µl of TE (Tris, EDTA) Buffer. The bacterial samples will be stored at -80 °C. Prior to shipment to Forsyth for HOMINGS analyses, genomic DNA will be

purified using the Master Pure Gram Positive DNA Purification kit (Epicentre Biotechnologies, Madison, WI, USA), with modifications (<http://mim.forsyth.org>). DNA samples will be sent on dry ice to Forsyth Institute. Per Forsyth Institute and the University of Michigan Office of Technology Transfer, a Material Transfer Agreement (MTA) will not be required prior to sharing of the samples.

HOMINGS:

At the Forsyth Institute, microbial profiles will be generated from image files of scanned HOMINGS microarrays (<https://homings.forsyth.org>). In brief, concentration levels of approximately 600 oral taxa will be determined by microarray hybridization using a fluorescent readout reverse-capture method.³⁶

Fluorescently labeled sample microbial DNA will be captured by 16S rRNA-based probes attached to glass slides. The fluorescent intensity for each probe will be scanned, normalized and scaled as previously reported.³⁶ Signals of 2× backgrounds will be considered to be negative and assigned a HOMINGS level score of 0. Positive hybridization signals will be categorized into five levels, with 1 indicating a signal that was just detectable, and 5 indicating maximum signal intensity.³⁷

Statistical Analysis:

Data will be analyzed using SPSS Pc+ version 22.0 statistical software. Descriptive statistics (mean, standard deviation, frequencies and percentages) will be used to describe the quantitative and categorical variables. Appropriate parametric statistical tests (one way analysis of variance followed by Tukey's test) and non-parametric statistical tests (Pearson's chi-square and Krushal Wallis test) will be used depending on the type and distribution of variables. A p-value ≤ 0.05 will be used to report the statistical significance of results.

Future Research:

Data and any samples remaining following HOMINGS analysis may be retained for future analysis/research. Subjects will provide or deny permission for their samples and data from this project to be used in future research in the informed consent document.

References:

1. Petersen PE, Yamamoto T: Improving the oral health of older people: the approach of the WHO global oral health programme. *Community Dent Oral Epidemiol* 2005; 33:81–92.

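### Prior SDF on the sampled tooth, professionally applied fluoride and recent scaling are neither washed out nor listed as recorded, so they can enter the only before/after contrast

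*Combined protocol and SAP*

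**What the plan says.** The Objective is a within-subject comparison of microbial deposits before SDF and one month after it. Under Exclusion Criteria, two items deal with recent exposures that could disturb the baseline sample: "Patients taking antibiotics within the last two weeks" and "Patients using chlorhexidine or fluoride mouth washes within the last two weeks". At lesion level, the Inclusion Criteria require "At least one tooth with active (soft) cavitated lesions of ICDAS score 5 or 6 near the gingival margin", and the exclusions remove "Teeth with arrested (hard) cervical or root caries lesions". Neither lesion rule refers to treatment history.

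The Introduction says SDF is approved in the USA. On frequency of use it says "Most studies recommend using SDF once a year to arrest caries", and it reports that "caries lesions might reactivate within the year if salivary function and oral hygiene is poor". Its paragraph on the assay says "HOMINGS can determine the efficacy of therapies/treatments, e.g., mouth rinses, antibiotic treatment, scaling and root planning, and laser or periodontal surgery".

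Outcome Measures and its Assessment gives the questionnaire topics as brushing, fluoride toothpaste, sweet snacks between meals, and acceptability of the treatment. Sample Size sets 20 subjects, and the Treatment section has one lesion sampled in each.

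**The concern.** A before/after comparison without a control group depends on the baseline sample. Whatever else altered the lesion's plaque shortly before baseline, or is still altering it during the month, appears as part of the change after SDF.

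The authors evidently accept this, since they wash out antibiotics and two kinds of rinse. The list stops short of three exposures that the same reasoning covers:

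- **Earlier SDF on the sampled tooth.** The baseline is then not a sample from a lesion unexposed to the study agent.
- **Professionally applied fluoride.** A fluoride rinse within two weeks disqualifies a patient, but fluoride applied in the clinic the day before does not. The plan gives no reason for the difference.
- **Scaling, root planing or periodontal surgery.** The plan names these beside rinses and antibiotics as treatments whose effect the assay can determine.

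The recruitment setting makes such exposures plausible. Subjects come from a dental school's clinics, some at a patient appointment, and the Introduction notes that "Root caries is common in institutionalized elders and periodontal patients with exposed root surfaces". At stake is whether an observed change, or its absence, can be attributed to the SDF applied in the study.

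**Working it through.** **Step 1. Text check.** Each exposure was compared with every rule that might catch it.

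| Exposure before baseline | Timed exclusion | Caught by the lesion criteria | Listed questionnaire topic |
|---|---|---|---|
| Antibiotics | Yes, two weeks | – | No |
| Chlorhexidine or fluoride rinse | Yes, two weeks | – | No |
| Earlier SDF, lesion now hard | No | Yes (arrested lesions excluded) | No |
| Earlier SDF, lesion still soft or active again | No | No | No |
| Professionally applied fluoride | No | No | No |
| Scaling, root planing, periodontal surgery | No | No | No |

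The fourth row follows from the plan's own text: it allows that lesions can reactivate, and a soft ICDAS 5 or 6 lesion meets the criteria whatever its history. Black staining is described under Study Subjects and Screening as an effect patients are told about, but no eligibility rule uses it.

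**Step 2. What could be reproduced.** The only relevant planning figure is 20 subjects. It cannot be reproduced, because the plan gives no effect size, standard deviation, power or dropout rate. The documents also give no frequency for any of these exposures. Steps 3 to 5 therefore rest on assumed inputs. The paired t-test is also an assumption, since the Statistical Analysis section does not name it.

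**Step 3. Exposed lesions that show no change.** Take a two-sided 5% paired t-test with n = 20. By the noncentral t distribution, 80% power needs a standardised change d = 0.66. Suppose a fraction f = k/20 of lesions shows zero change because of earlier SDF, which is a worst case for those lesions. Then

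- mean change = (1 − f)d
- SD = √(1 + f(1 − f)d²)

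| k of 20 | Mean | SD | Mean/SD | Power |
|---|---|---|---|---|
| 0 | 0.660 | 1.000 | 0.660 | 80% |
| 2 | 0.594 | 1.019 | 0.583 | 70% |
| 3 | 0.561 | 1.027 | 0.546 | 64% |
| 4 | 0.528 | 1.034 | 0.511 | 58% |

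Simulation with exactly k unchanged lesions gives the same power figures to the nearest percentage point.

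**Step 4. Exposed lesions that shift for another reason.** Suppose SDF has no effect, but exactly 4 of 20 lesions change by 1 SD because of a recent procedure. The mean change is then 4/20 × 1 = 0.2 SD. In one million simulated trials the nominal 5% test rejects in 10.5%, or about 11%.

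**Step 5. Chance that at least one exposed lesion enters.** If a proportion p of eligible lesions is exposed, the chance of at least one among 20 is 1 − (1 − p)²⁰. For p = 2%, 5%, 10% and 20% this is 33%, 64%, 88% and 99%.

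**The case against.** The strongest reply is that the plan already guards against most of the prior-SDF problem. Lesions must be soft and active, hard ones are excluded, and the investigator inspects and probes each lesion. Earlier SDF leaves black staining, and pre-treatment photographs are taken when possible. Reactivation is described as conditional on poor salivary function and hygiene, while this trial enrols generally healthy adults. US approval and a yearly recommendation do not show that these patients have had SDF. All of this stands: it narrows the route and may leave few such lesions. It does not close it, and it does nothing about scaling or professional fluoride.

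A second reply is that the consequences are not documented. This also largely stands. A reader might infer that plaque after scaling re-matures over the month and imitates a treatment effect, or that previously treated lesions necessarily pull the result towards nil. The documents support neither. The assay paragraph lists uses of the method; it does not say how scaling alters plaque on a cavitated cervical lesion, or for how long. They also state no specific effect of professional fluoride on the baseline sample. The possible biases can run in opposite directions.

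A third reply is that the questionnaire itself is not in the documents and may ask about dental history. That is possible. The plan as written does not list it, and no eligibility rule would act on the answer.

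**Conclusion.** The gap is real and worth correcting before enrolment. Applied as written, the entry criteria can admit subjects whose baseline follows earlier SDF on the same tooth, professional fluoride or scaling. In a single group of 20 with one lesion each, these influences cannot be separated from the SDF effect. Unless the exposures are recorded, they cannot be examined afterwards either.

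A reader might go further and infer that baselines in this trial are contaminated, or that the result is biased in a known direction. The documents do not support that, because frequency and net direction are both unknown. The power losses (80% to about 70% to 58%) and the error rate of about 11% show only how sensitive a study of this size would be under the assumed inputs. They are not estimates for this trial.

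**What to change.** Amend the Exclusion Criteria in two places:

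1. Exclude from sampling any tooth previously treated with SDF or another silver product.
2. Add a wash-out before the baseline sample for professionally applied fluoride, and one for scaling, prophylaxis or periodontal surgery. The investigators should set and justify the windows, since the documents give no basis for a particular length.

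Check both from the dental chart for every subject. Chart review is at present only one of two referral routes, so it would have to become a fixed step. Add one question on these exposures to the baseline questionnaire and record the dates. In the Statistical Analysis section, add a sensitivity analysis that omits any subject found to have been exposed.

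The cost is one amendment, a chart check per subject and one extra question. Some candidates will be excluded or deferred; the documents do not allow their number to be estimated.

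### The hypotheses credit a one-month fall in lesion bacteria to 38% SDF, but all 20 participants also get a hygiene package and there is no comparator, so the change cannot be attributed to SDF alone

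*Combined protocol and SAP*

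**What the plan says.** The Hypothesis section sets the null as "there is no inhibitory effect of bacteria by 38% SDF" and the alternative as "there is an inhibitory effect of bacteria by 38% SDF". These are the only hypotheses in the document. The Research Question asks: "What is the mechanism of action of silver diamine fluoride (SDF) on bacteria involved in root or cervical carious lesions".

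The Objective says that the effect will be assessed by "assessing microbial deposits on root or cervical caries lesions before and 1 month after SDF application". Outcome Measures and its Assessment gives the purpose of the two visits as "to compare the microbial composition of bacterial samples at the two different stages". Sample Size sets 20 subjects, and Treatment has plaque taken from one randomly chosen eligible lesion in each.

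SDF is not the only thing given. Study Subjects and Screening adds: "Individualized oral hygiene instructions will be provided to each participant, focusing on effective brushing with a manual toothbrush", and then "use of fluoride toothpaste will be recommended". Under Incentives: "Participants will be given a toothbrush and toothpaste at the initial visit". These three items are called the package below.

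**The concern.** The hypotheses name one cause. The data will show the change after that cause, the package and a month of elapsed time have all acted. If the p-value threshold in Statistical Analysis is met, the only hypothesis available to reject is the one about 38% SDF, and nothing in the plan tells the author to say less. A thesis or paper could then state that SDF reduced the bacteria when the study cannot tell SDF from better brushing, fluoride toothpaste or ordinary variation over the month.

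The research question has a second, separate difficulty. It asks how SDF acts, while the measurements record which bacteria are present and at what level.

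**Working it through.** The plan gives no effect size, standard deviation or power behind its 20 subjects, so there is no figure to reproduce. The check sets the sections side by side.

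1. **Who receives what** (Study Subjects and Screening, Treatment, Sample Size, Incentives).
   - SDF and package: 20
   - SDF without package: 0
   - Package without SDF: 0
   - Untreated control lesion: none described

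   The two calibration subjects in Sample Size give a test plaque sample to check the sampling technique; they are not a comparator. A figure just before Treatment is not shown, but no surrounding text points to a control group.

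2. **What each patient's change contains.** Written additively for simplicity, change = SDF part + package part + other change over the month. The mean over 20 patients estimates the sum of the three mean parts. A test that this sum is zero tests the SDF part only if the other two sum to zero, and nothing in the documents establishes that. More patients would estimate the same sum more precisely without dividing it.

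3. **Does anything else in the plan separate the parts?**
   - The exclusions for antibiotics, chlorhexidine and fluoride mouthwash in the previous two weeks apply at entry. They do not touch a package given at the first visit.
   - Questionnaires at both visits cover brushing, fluoride toothpaste and snacking. Statistical Analysis names no use for them. Uptake of advice can differ between patients, so they carry some information, but self-report from 20 people who all had the same advice and the same SDF could not reliably isolate SDF.
   - Statistical Analysis plans no adjustment and states no limit on attribution.

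4. **What the Introduction says about the package.** It holds that hygiene instruction should in theory help, since plaque bacteria cause root caries, and it reports a trend to less new root caries with SDF plus education than with SDF alone. It also cites one study in which SDF prevented new root caries better than hygiene instruction alone, and another in which SDF plus education did better than instruction alone. All of these are caries outcomes, not bacterial ones. Together they give reason not to ignore the package and no basis for sizing it.

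5. **Illustration with assumed values.** Suppose that SDF had no effect and that package or time shifted the outcome by d standard deviations of the paired differences. For a two-sided paired t-test at 0.05 with n = 20, the rejection probability comes from the noncentral t distribution with 19 degrees of freedom and noncentrality d × √20. The test and every d are assumptions; the plan names no paired test.

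| d | d × √20 | Probability of rejecting no change |
|---|---|---|
| 0 | 0 | 0.05 |
| 0.2 | 0.89 | 0.14 |
| 0.3 | 1.34 | 0.25 |
| 0.5 | 2.24 | 0.57 |
| 0.8 | 3.58 | 0.92 |

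   With n = 40, the values at d = 0.3 and 0.5 rise to 0.46 and 0.87. The 0.05 threshold protects the statement that nothing changed; it does not protect the statement that SDF did nothing.

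6. **Mechanism.** The HOMINGS section yields a level score for each of about 600 taxa. Two such profiles show which taxa rose or fell. They would not show how SDF acts even if a randomized control group were added, so this problem is distinct from attribution.

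**The case against.** A single-group before-and-after study of 20 is a legitimate exploratory choice for a thesis, and the Objective is open about its timing. No estimate or test result would change under the proposed wording. All of that stands, and it is why the point concerns what is claimed and asks for no control arm.

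Statistical Analysis contains no rule tying a given test to the null hypothesis or dictating how a result is reported. A reader might infer that the plan prescribes an SDF-specific or mechanistic conclusion; it does not. It leaves that conclusion as the natural one, because no other hypothesis is stated and no limit on interpretation is given.

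A reader might also infer that the package probably explains any change. The documents do not support that: in the caries studies cited in the Introduction, SDF-based care did better than instruction alone. SDF may well dominate, but this study cannot test that belief.

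**Conclusion.** The point holds as a mismatch between hypothesis and design. All 20 participants are to receive SDF and the package together, and one combined change is estimable. A significant result would support a change after the combined treatment over one month. It would not support an effect of 38% SDF alone. The size and direction of any non-SDF part are unknown; the conclusion needs no assumed value for them, and the probabilities in the illustration are not estimates for this trial. It rests on the text describing no comparator group or control lesion.

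Two stronger readings should be resisted. One is that the design is invalid or must gain a control group: the data remain useful as a description of change. The other is that the mechanism question fails because of confounding: it fails because taxon profiles do not measure mechanism, and a control would not cure that.

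**What to change.** - **Hypotheses.** Keep the inhibitory direction and name the whole treatment. For example, H_0: no reduction in lesion bacterial levels from baseline to one month after SDF given with oral hygiene instruction and a fluoride-toothpaste recommendation; H_A: there is a reduction. A looser alternative of any change in composition would drop the direction without need, since composition can shift without inhibition.
- **Objective.** Align it with the same wording.
- **Statistical Analysis.** Add one sentence: a significant change will be reported as change after the combined treatment and not as an SDF-specific effect, because the single-group design does not separate SDF from the package or from time.
- **Research Question.** Separately, replace the reference to mechanism with change in lesion bacteria.
- **Questionnaires.** Tabulate the brushing, fluoride-toothpaste and snacking answers from both visits descriptively, as context and not as an adjustment.

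The cost is a few sentences and one table of data already to be collected. The study gives up the SDF-only causal claim and the mechanism question. Care, visits, sampling and enrolment stay as they are.
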